7.2 Study Procedures

Provide a description of all research procedures being performed and when they are being performed (broken out by visit, if applicable), including procedures being performed to monitor subjects for safety or minimize risks. Include any long-term follow-up procedures and data collection, if applicable.

Describe where or how you will be obtaining information about subjects (e.g., medical records, school records, surveys, interview questions, focus group topics, audio or video recordings, data collection forms, and collection of specimens through invasive or non-invasive procedures to include the amount to be collected and how often). Add any data collection instruments that will be seen by subjects to your study in CATS IRB (<http://irb.psu.edu>) in the "Supporting Documents" page.

7.2.1 EXAMPLE: Visit 1 or Day 1 or Pre-test, etc. (format accordingly)

Provide a description as defined above and format accordingly.

Online surveys using Qualtrics will be administered at the time when researchers sign-up to participate in the RPC. Survey instruments are provided as a supporting document. The survey asks for demographic information and about prior policy experiences, recent policy engagement, policy-informed research activities, perceptions about engaging public officials, perceived self-efficacy engaging with public officials, reported policy knowledge and training needs, satisfaction in collaborating with public officials, value and impact of partnering with public officials, and trust and respect within researcher-public official partnerships.

Qualitative interviews will occur prior to RPC implementation at the time of study enrollment. Interviews will occur by web-chat or phone, and will ask:

- What are your experiences of working with policymakers? What worked well? What were some of the challenges?
- What do you think the most useful kinds of evidence are for policymakers? Can you give examples?
- What types of interactions or initiatives do you think would be most helpful to link researchers and policymakers?

7.2.2 EXAMPLE: Visit 2 or Day 2 or Post-test, etc. (format accordingly)

Provide a description as defined above and format accordingly.

The same survey protocol as used in the pre-test will be administered approximately every three months for about one year: (2) Subsequent to training, (3) Subsequent to policy engagement, and (4) Follow-up. Efforts to minimize survey attrition will include tracking non-responses to follow-up surveys and requesting survey participation via individual emails twice per week until survey completion or until the 3-week window for survey participation ends or until the participant opts-out of participating in the survey. In the last week of the survey window, survey participants who have not yet participated or opted-out of participation will be contacted by phone to request their participation and to complete the survey over the phone if needed.

Qualitative interviews will occur subsequent to the RPC implementation, approximately 9 months following study enrollment, using web-chat or phone. These interviews will ask:

- How did you become involved in the RPC? Is this your first involvement with policy? With legislation? If no, what are your previous experiences?

- What were your expectations and aspirations from involvement in the RPC?
- Can you describe the interactions you've had with policymakers through the RPC? (e.g. informal coffees, phone calls, formal meetings, etc). How does this compare to interactions outside the RPC?
- What kinds of evidence have you seen and used as part of the RPC? How? Did this reflect your expectations?
- What has worked well? What could have gone better? (Risks of interaction, perceptions and stereotypes)

This study also involves non-human research data, drawing from public information regarding public officials' use of research evidence, which will be obtained from legislators' sponsored bills, public statements, and reported research use by public officials. Non-human research data will also support the interpretation of key findings from the current investigation that involve human subjects.

This study also involves human research data that are exempt from consent processes. This involves observations of public meetings occurring through the RPC, including researcher trainings and meetings between researchers and public officials' offices. Observations involve minimal risk to subjects because the probability of harm or discomfort from the collection of observational data from public meetings is not greater than participating in the public meeting with no observation. Meeting attendees voluntarily elect to participate in these meetings, and meeting participants have complete control regarding with whom or the extent to which they share personal information. Meeting participants have the right to end participation in the observed meeting at any time. The observation of public meetings is unobtrusive, as the observer will join the meeting in a similar manner as the meeting participants. Meeting durations are expected to last around 30 minutes; therefore, a written consent procedure would detract time from the meeting itself. Furthermore, written consent procedures would disrupt the nature of interactions that are of focus in the observation. No pertinent information of value to meeting participants will be gleaned from the observation. Observational data involve unstructured, qualitative field notes regarding natural processes and interactions that occur during the intervention. These public research data are process-oriented to enable internal evaluation and inform improvements to the RPC.

7.3 Duration of Participation

Describe the duration of an individual subject's participation in the study.

Study participation lasts for up to two years or until the participant opts-out of the study.

8.0 Subject Numbers and Statistical Plan

8.1 Number of Subjects

Indicate the total number of subjects to be accrued.

If applicable, distinguish between the number of subjects who are expected to be enrolled and screened, and the number of subjects needed to complete the research procedures (i.e., numbers of subjects excluding screen failures.)

We aim to enroll a maximum of 300 researchers in the baseline period of this study. The target number of study participants in the full study is 80, including 40 researchers in the intervention and 40

researchers in the control group. This level of oversampling is required because not all researchers will complete all phases of the intervention and oversampling will combat attrition from study participation.

Twenty-two researchers from the intervention group will be selected to participate in depth-interviews (11 at pre-test and 11 at post-test). Researchers will be sampled purposively such that the sample is representative of those with or without prior policy experience and range in their attitudes toward policy engagement (e.g., skeptical or positive), which will be determined by survey data from the first time point.

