Those in the RPC group who have expertise related to current congressional priorities and needs may be invited to participate in a Rapid Response Event, which brings researchers and congressional staff together face-to-face to meet in congressional offices (Washington, DC) and plan a collaborative response to a current policy issue. To clarify expectations for involvement and minimize the threat of disappointing those who are not invited to the Rapid Response Event, all RPC participants are repeatedly informed throughout the capacity-building stage (via trainings and the discussion forum) that this selection process will occur based on their participation in trainings, web-based engagement, and a match between their expertise and congressional needs. Subsequent to these meetings, RPC participants work collaboratively with one another and the congressional office to respond to the current policy issue.

Participation in the study is voluntary among those enlisting in the RPC; opting out of the survey will not impact their ability to participate in the intervention. Study participants are asked to complete the survey approximately every three months for about one year: (1) Baseline, (2) Subsequent to training, (3) Subsequent to policy engagement, and (4) Follow-up. Twenty-two study participants in the intervention group will be asked to complete in-depth qualitative interviews regarding their experiences: 11 will participate prior to RPC involvement and 11 will participate subsequent to their RPC involvement. Qualitative interviews will be recorded and transcribed.

Observations of public meetings may involve three types of participants: (1) public officials, (2) researchers who have consented to study participation, and/or (3) researchers who are involved in the intervention but did not consent to study participation. Public meetings include: (1) those that occur in

public officials' offices, which are located in congressional office buildings that are open to the public (i.e., any member of the public may visit any office at any time), and (2) online trainings that are open to the public, accessible through a URL on a publicly available website.

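### All 22 in-depth interviews go to the intervention arm, and half may precede survey 4, so any effect of interview contact on self-report is counted as RPC effect; the bias is partial and of unknown size

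*Protocol*

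**What the plan says.** Protocol 7.1 and 8.1 agree on who is interviewed. Section 7.1 has "Twenty-two study participants in the intervention group will be asked to complete in-depth qualitative interviews regarding their experiences", and 8.1 gives the same number with the split: "Twenty-two researchers from the intervention group will be selected to participate in depth-interviews (11 at pre-test and 11 at post-test". No section offers an interview to controls. Selection is purposive, on prior policy experience and attitude to policy engagement, "which will be determined by survey data from the first time point".

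On timing, 7.2.1 has "Qualitative interviews will occur prior to RPC implementation at the time of study enrollment", and 7.2.2 has "Qualitative interviews will occur subsequent to the RPC implementation, approximately 9 months following study enrollment, using web-chat or phone". The surveys follow their own schedule: "Study participants are asked to complete the survey approximately every three months for about one year", four in all, with a three-week response window for each follow-up survey (7.2.2). Nothing says whether survey 4 or the late interview comes first.

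Section 15.1 puts the interview at an additional hour and the survey at about 20 minutes. Section 8.3 plans longitudinal models over the four time points. The SAP (Data Analysis Plan) plans logistic models for three researcher outcomes: knowledge of lobbying restrictions, belief that engagement would improve one's own research, and level of policy engagement. Neither document includes a term, exclusion or sensitivity analysis for interview contact.

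**The concern.** The interviews are a research procedure. The RPC as described in 7.1 consists of webinars, a forum, requests to contribute to policy work, and for some participants the Rapid Response Event. An interview is none of these, yet only RPC participants receive one.

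The questions ask people to reflect on working with policymakers and, in the late set, on how their RPC contacts compare with others. The survey asks the same people about their engagement with officials and their views of it. Talking a subject through for an hour can change how a person later rates it, in either direction. Section 5.1.2 already treats these survey answers as open to social desirability, and uses that to justify keeping participants unaware of their condition.

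At stake is the meaning of the arm difference. With contact in one arm only and no allowance for it in the analysis, an interview effect cannot be told apart from an RPC effect in the planned models.

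**Working it through.** The plan states no figure for an interview effect, so there is nothing to reproduce. The check has three parts.

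**1. Order of events.** Interviewees belong to the intervention group and are chosen from baseline survey answers. The early interview therefore follows both assignment and survey 1, and precedes surveys 2, 3 and 4. Three-month spacing puts the surveys at months 0, 3, 6 and 9. The phrase about one year allows survey 4 to fall as late as about month 12. With the late interview at about month 9:
- survey 4 near month 12: the interview comes first;
- survey 4 near month 9: either may come first.

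So 11 interviews can affect surveys 2 to 4, and up to 11 more can affect survey 4 only.

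**2. Size.** Shift in the arm difference = (interviewed ÷ analysed in the intervention arm) × interview effect in SD.

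Inputs:
- 40 per arm: the target (Protocol 8.1; SAP).
- 225 at baseline and 112 completing (Protocol 16.2; SAP). With 1:1 allocation, which is an assumption, 225/2 = 112.5 and 112/2 = 56 per arm.
- Interview effect of 0.1 to 0.3 SD: an assumption. The SD scale is only a rough guide, because the SAP uses logistic models for these outcomes.

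Every interviewee analysed, and every late interview before survey 4:

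| Per arm | Share interviewed | Shift at survey 4 (SD) |
|---|---|---|
| 40 | 22/40 = 55% | 0.055 to 0.165 |
| 56 | 22/56 = 39% | 0.039 to 0.118 |
| 112.5 | 22/112.5 = 20% | 0.020 to 0.059 |

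Early interviews only (surveys 2 and 3, and survey 4 if it precedes the late interviews):

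| Per arm | Share interviewed | Shift (SD) |
|---|---|---|
| 40 | 11/40 = 27.5% | 0.028 to 0.083 |
| 56 | 11/56 = 20% | 0.020 to 0.059 |
| 112.5 | 11/112.5 = 10% | 0.010 to 0.029 |

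Early interviewees dropping out like everyone else (half, an assumption drawn from 16.2), 56 completers per arm:
- early only: 5.5/56 = 9.8%, shift 0.010 to 0.029 SD;
- plus all 11 late interviewees: 16.5/56 = 29%, shift 0.029 to 0.088 SD.

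For scale, the plan cites an effect size of 0.2 (Protocol 8.2; SAP). To produce a difference of 0.2 at survey 4 unaided, the interview effect would have to be 0.2/0.55 = 0.36 SD at 40 per arm, 0.2/0.393 = 0.51 at 56, or 0.2/0.196 = 1.02 at 112.5.

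**3. Can the data reveal it?** Only roughly. Comparing 11 early interviewees with the other 45 of 56 in the intervention arm has an unadjusted standard error of √(1/11 + 1/45) = 0.34 SD, larger than the whole assumed range. A null result there would not show that the interviews had no effect.

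**The case against.** The case for leaving the design alone has weight.

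- **Purpose.** The interviews study how RPC partnerships work. Controls have no RPC interactions, so most of the post-test questions would mean little to them. This stands, and the proposal does not ask for late interviews with controls.
- **Overlap.** No listed question concerns lobbying restrictions, or asks whether engagement improves one's own research. The overlap is with engagement and general views on working with policymakers. This stands: the concern reaches some outcomes more than others, and the knowledge outcome least.
- **Dose.** One hour is little beside six one-hour webinars and possible meetings in congressional offices. This bears on size only. The webinars are the treatment under test; the interview is not.
- **Blinding.** The pre-RPC questions do not reveal assignment, and both arms answer the same four surveys, so reactivity to the surveys is balanced. Both points are correct. The argument from section 5.1.2 is therefore limited: it shows that the plan regards these answers as reactive, not that the interviews unblind anyone.

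A reader might infer more than the documents support. One such reading is that every late interview precedes survey 4; on a 0/3/6/9 schedule it could follow, and would then bias nothing. Another takes 40 per arm, all 22 interviewees retained and an effect of 0.2 SD, giving 0.2 × 0.275 = 0.055 to 0.2 × 0.55 = 0.11 SD, or 28 to 55% of the cited effect size. That combines the smallest denominator with full retention and an assumed effect, and cannot stand as the expected bias. Nor is the RPC comparison wholly confounded, since on the plan's expected numbers most of the intervention arm is never interviewed.

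**Conclusion.** The concern holds in a limited form. Interview contact differs by arm, part of it certainly precedes outcome surveys and part of it may, and no analysis deals with it. The sign and size of the resulting bias are unknown. The survey-4 range runs from about 0.01 SD (early interviews only, 112 per arm, effect 0.1 SD) to 0.165 SD (all 22 before survey 4, 40 per arm, effect 0.3 SD). It rests on the assumed interview effect, 1:1 allocation and, in the tables, full retention of interviewees. It is modest unless the analysed arm is near 40. This does not invalidate the trial. It deserves action because the plan aims at effects as small as 0.2 and because the late part can be removed with almost no effort.

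**What to change.** **Late interviews.** State in Protocol 7.2.2 that a participant's post-test interview is held only once that person has submitted survey 4 or its three-week window has closed. This removes the late part of the bias and loses no interview. The cost is interviews up to about three months later, with slightly older recall. If survey 4 falls near month 12, the timing must be coordinated with the debriefing at about one year (5.1.2). Participation may last up to two years (7.3), so there is room.

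**Pre-RPC interviews.** Choose one and write it down.
1. Accept the limitation and add to the SAP a sensitivity analysis for interview contact that adjusts for the baseline policy experience and attitudes used in selection. Label it a non-randomised comparison. Simply dropping the interviewees is not advised: they were chosen purposively and all come from one arm, so their removal breaks the randomised comparison. If any late interview precedes survey 4, the analysis should cover all 22 at that survey.
2. Optionally, include some controls. The three pre-RPC questions do not depend on arm and would not disclose it. Eleven cannot be halved, so the split would be 6/5. If the interview effect is the same in both arms, the early imbalance falls to one person: at most 0.3 × 1/40 = 0.0075 SD at 40 per arm. The cost is a thinner qualitative sample, with five or six early interviews left in the intervention arm, and matching edits to 7.1 and 8.1.

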8.2 Sample size determination

If applicable, provide a justification of the sample size outlined in section 8.1 – to include reflections on, or calculations of, the power of the study.

Statistical analyses are all powered at least at a 90% level to detect effect sizes of 0.2 or greater (power analysis conducted with *Optimal Design plus Empirical Evidence*).

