8.3 Statistical methods

Describe the statistical methods (or non-statistical methods of analysis) that will be employed.

Surveys data will be analysed longitudinally by modelling change across 4 time points—including repeated measures and multilevel growth curve models (MLM) using *MPlus*. Missing data will be handled with multiple imputation.

Qualitative interview data will be analyzed using a thematic process followed by an intensive discourse analysis. Data will be interpreted alongside observational data using an interpretive policy analysis to develop a data-driven theoretical framework for describing evidence use in the RPC.

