16.2 Feasibility of recruiting the required number of subjects

Indicate the number of potential subjects to which the study team has access. Indicate the percentage of those potential subjects needed for recruitment.

It is anticipated that around 300 researchers will be recruited for the RPC. We believe that at least $\frac{3}{4}$ ($n = 225$) of those may participate in the study at baseline, and approximately half of those individuals may complete the study ($n = 112$), which would over-sample for the current study.

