All data will be handled in accordance with the consent procedures and IRB protocol. Identifiers will be stripped from the data files for archival storage. Identifying information will be destroyed within three years of the end of the project. De-identified study data will be archived indefinitely. Identifying info will be destroyed within three years of the end of the project.

Analyses for survey outcomes for researchers and legislative staff follow similar patterns and will be conducted in *MPlus* or *SAS*. For researchers, logistic models will be used to model researchers' change from baseline in 1) knowledge of current lobbying restrictions, 2) belief that engaging with policymakers would improve their own research, and 3) level of policy engagement. For legislative staff, generalized linear models will be used to model the trial groups on how much congressional offices value URE for 1) conceptual, 2) instrumental, and 3) tactical purposes

For legislative offices, we will assess the impact of the RPC on both proposed and enacted bills. Since the continuity of relevant legislative activity may be inconsistent between short intervals due to Congressional recesses (e.g., 3-month survey timeframes), legislative activity will be analyzed and compared between two time periods: one-year before RPC implementation (baseline) and six months following RPC implementation (post-assessment). The indicators for evidence use in this

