project will reflect having used research evidence language in legislation related to the wellbeing of children and families, as determined by trained coders, on which the office is listed as a sponsor or original cosponsor. This outcome is dichotomous: did or did not sponsor or originally cosponsor legislation that was coded as having used research evidence. Therefore, logistic regression analyses will assess use of research evidence. Given the cyclical nature of Congress, it is expected that overall legislative productivity will be different at baseline than at the post-assessment. Thus, the control and intervention groups will be compared to one another at each timepoint separately. They will be compared at baseline to establish if there is a difference in sample, perhaps due to self-selection biases. If there is no difference at baseline, we will compare the use of research evidence in legislation among control offices and intervention offices at the post-assessment time period. We will regress dichotomous post-assessment use of research evidence on group assignment. Similar logistic regressions will be conducted on the probability of an office writing 1) a bill related to the wellbeing of children and families and 2) a bill that did not include URE research evidence terms.

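### The stated 90% power for an effect of 0.2 in all analyses cannot be reproduced; at 80 to 112 completers it fails for a 0.2 SD difference between arms (correlation up to 0.7) and for the SAP's logistic researcher models

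*Protocol*

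**What the plan says.** Protocol 8.2 (Sample size determination) and the SAP (Sample Size Justification) carry the same sentence: "Statistical analyses are all powered at least at a 90% level to detect effect sizes of 0.2 or greater". Only the software is named.

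On numbers, Protocol 8.1 says "The target number of study participants in the full study is 80", split 40 and 40, with at most 300 enrolled at baseline. Protocol 16.2 expects 225 at baseline, of whom "approximately half of those individuals may complete the study", which it puts at 112. The SAP repeats these figures.

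On methods, Protocol 8.3 plans repeated-measures and multilevel growth models over four survey waves, and "Missing data will be handled with multiple imputation". The SAP (Data Analysis Plan) names a different model class for this group: "For researchers, logistic models will be used to model" change in three outcomes. It adds two analyses with no sample size in either document. One is for staff: "For legislative staff, generalized linear models will be used to model the trial groups". The other is for legislative offices: "We will regress dichotomous post-assessment use of research evidence on group assignment".

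**The concern.** This sentence is the only power justification in either document, and it is both quantified and universal. A difference of 0.2 SD is small, and 40 to 56 people per arm is far fewer than such a difference usually needs. If the figure is wrong for the planned models, a non-significant result could be read as evidence against an effect of 0.2 that the trial had little chance of detecting. If 0.2 is on some other scale, the reader cannot tell what difference between arms the study was sized for.

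**Working it through.** **Inputs from the documents.** N = 80 (40 per arm) and at most 300 (Protocol 8.1); 225 at baseline and 112 completers (Protocol 16.2); four waves, so three follow-ups (Protocol 8.3).

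**Assumed, because not stated.** Two-sided 5%, 1:1 allocation, equal correlation r between waves of 0.5–0.7, outcome SD of 1.

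**1. The plan's own figure.** It cannot be reproduced, because the metric, alpha, model and N behind it are missing. The steps below test the standard readings.

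**2. 0.2 SD, unadjusted.** The noncentrality is 0.2·√(N/4): 0.2·√20 = 0.894 at 80 and 0.2·√28 = 1.058 at 112. Power is 14% and 18%. For 90%, 526 per arm (1,052 in total) are needed.

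**3. 0.2 SD, mean of three follow-ups adjusted for baseline.** The variance factor is V = (1 + 2r)/3 − r², which is 0.417 at r = 0.5 and 0.310 at r = 0.7. The noncentrality is 0.2·√(N/(4V)). At N = 80 this is 0.2·√(20/0.417) = 1.39 and 0.2·√(20/0.310) = 1.61. At N = 112 it is 1.64 and 1.90.

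**4. 0.2 SD at the last wave of a linear growth model, no random-slope variance.** The slope difference is 0.2/3 = 0.067 per wave, and the slope variance per person is (1 − r)/5. At N = 80 the noncentrality is 0.067·√(20/0.10) = 0.94 at r = 0.5 and 0.067·√(20/0.06) = 1.22 at r = 0.7.

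| Power for 0.2 SD, r = 0.5–0.7 | N = 80 | N = 112 | N = 225, fully observed |
|---|---|---|---|
| Adjusted mean of three follow-ups | 28–35% | 37–47% | 64–77% |
| Last wave, linear growth | 15–23% | 20–30% | 35–53% |

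At 300 fully observed, the first row becomes 76–87%. Higher correlation helps. At r = 0.9 the adjusted mean gives 71% at 80 and 85% at 112; at r = 0.85 it gives 94% at 225 fully observed.

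**5. The SAP's logistic researcher models (two-arm approximation without baseline adjustment).**
- *Odds ratio matching 0.2 SD.* exp(0.2·π/√3) = 1.44, log 0.363. With a control rate of 50% the other arm has 59.0%. At 40 per arm the standard error is √(1/(40·0.5·0.5) + 1/(40·0.59·0.41)) = 0.451, so z = 0.363/0.451 = 0.80 and power is 13%. Over control rates of 20–50%, power is 10–13% at 80, 13–16% at 112 and 21–27% at 225.
- *Cohen's h = 0.2.* 14% at 80 and 18% at 112.
- *A 20-point risk difference, control rate 10–50%.* 43–61% at 80 and 56–76% at 112, taking the log-odds Wald and pooled-proportion formulas together. At 225 fully observed the Wald formula gives 85–95%.
- *With baseline adjustment.* In simulations of a 0.2 SD latent shift, a baseline-adjusted logistic model gave about 8–13% at 80 and 12–16% at 112. The mean of three binary follow-ups, adjusted for baseline, gave 14–19% and 21–26%.

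**6. Readings of 0.2 that do come near 90%.**
- *Cohen's f = 0.2 as a main effect of arm.* With two equal arms d = 2f = 0.4 SD. In the model of step 3, power is 78–89% at 80 and 90–97% at 112.
- *A growth-rate difference of 0.2 SD per wave.* This is 3 × 0.2 = 0.6 SD at the last wave. Without random-slope variance, power is 80–95% at 80 and 91–99% at 112. With an assumed random-slope variance of 0.02 it is 72–88% and 86–96%.
- *Cohen's f = 0.2 for group by time.* λ = f²·N·4/(1 − r) on 3 and 3(N − 2) degrees of freedom gives 86–99% at 80 for r = 0–0.5. This f equals 0.92 SD between arms if constant over follow-up, or 1.07 SD at the last wave if linear.

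**The case against.** The plan never says that 0.2 is a standardised mean difference, so the shortfall depends on the reading. An ordinary alternative, main-effect f = 0.2, meets the claim at 112 completers and corresponds to only 0.4 SD. This stands. A reader might infer that no reading reaches 90%, or that only very large effects could have been meant, and neither inference is supported. It does not rescue 'all', because none of the readings in step 6 applies to the logistic models.

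The correlation range is an assumption, and waves about three months apart could correlate more strongly. This also stands, and the result for 0.2 SD is therefore limited to r up to 0.7. Even at r = 0.9, though, two-sided power at 80 and 112 stays below 90%.

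Completers are not necessarily the analysis set, since imputation is planned. The figures at 80 and 112 may therefore understate power. Imputation cannot recover more than full observation of everyone enrolled. At the 225 expected and r up to 0.7, that bound stays below 90% for 0.2 SD, and it is 21–27% for an odds ratio of 1.44 in the approximation without baseline adjustment. Only the 20-point risk difference can reach 90% there.

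Event rates are not given. By the normal approximation, a 20-point difference reaches 90% at 112 if the control rate is about 2–3% or lower. The result for that metric should be read as applying to control rates of about 5% or more.

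**Conclusion.** The concern holds with those limits. The main defect is under-specification: a universal power figure without the inputs needed to check it. Under the most natural reading, 0.2 SD between arms, power at 80 to 112 completers is below 50% in both repeated-measures analyses tested with r up to 0.7. The logistic researcher models fall short of 90% on each metric tested, within the control rates stated. The readings that do reach about 90% correspond to differences of about 0.4–1.1 SD, and the documents do not say which, if any, was meant.

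A reader might go further and infer that the trial is too small, or that the sponsor's software run was wrong. The documents support neither. They name no smallest difference of interest, and they do not show the run's inputs. For the legislative analyses in the SAP, no power claim can be checked at all. The sentence needs correcting as it stands, because it is the only justification of sample size and restating it is cheap.

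**What to change.** In Protocol 8.2 and the SAP, replace the sentence with the effect detectable at 90% power for each planned researcher model. State the metric, alpha, N (completers, or with imputation), correlation or control rate, and test, using the sponsor's own inputs. If the original run used another metric, name it and give the equivalent difference between arms. In the SAP, delete 'all' or give N and power for the legislative-staff and legislative-office analyses.

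As an illustration only (two-sided 5%, 1:1, r = 0.5–0.7, completers only), the difference detectable with 90% power in the adjusted mean of three follow-ups is 0.41–0.47 SD at 80 and 0.34–0.40 SD at 112. For a binary outcome (unadjusted Wald, control rate 20–50%) the detectable odds ratio is about 4.8–6.0 at 80 and 3.7–4.0 at 112.

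The cost is a wording change in two places and a less favourable stated figure. The change does not settle whether the sample size is adequate.
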